**Methods:** Following baseline assessment, participants will be randomized to BWTraining at 2 months (Immediate group) or 1-year post-stroke (Delayed group). The intervention consists of 18 sessions (3X/week for 6 weeks) of BWTraining: 20–30 minutes of step training using a Body Weight Support and Treadmill system (BWST) followed by 15 minutes of overground gait training delivered by a physical therapist-led team. Participants will walk backward overground with assistance as warranted to transfer stepping skills from the BWST environment to overground. The Immediate group will be followed prospectively for 1-year and compared to the Delayed group to determine the effectiveness of BWTraining in decreasing falls (Specific Aim#1). BWSpeed post-intervention will be compared between groups to assess the timing effect of BWTraining (Specific Aim #2). The Delayed group will be followed prospectively for 1-year prior to BWTraining, to determine if BWSpeed at 2-months is a predictor of fall incidence in the first year post-stroke (Specific Aim #3).

Outcome Measures: Fall incidence 2-months to 1-year post-stroke is our primary outcome measure. Secondary measures include forward and backward walking gait speed, dynamic balance measured by the Functional Gait Assessment, fall self-efficacy measured by the Activities-Balance Confidence Scale and gait kinematics.

Data Analysis Plan: The total number of falls per patient month for the immediate and delayed intervention groups will be calculated, and using a nonparametric ratio estimate, point and interval estimates for the average hazard for each group will be determined. The ratio of the two individual group estimates, 95% confidence limits and P-values will be obtained. Forward stepwise ordinal logistic regression will be used to determine the independent relationship between BWSpeed at 2-months post-stroke and 1-year fall incidence of those in the Delayed intervention group.

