### **Backward Walking Training is an Emerging Intervention for Post-Stroke Gait.**

BWTraining has been used as a strategy in the rehabilitation of orthopedic conditions as it produces less mechanical strain on the knee joint and it is an effective means for increasing the strength and power of the quadriceps. BWTraining is also an option to improve aerobic capacity as backward walking can increase energy expenditure to levels high enough to maintain cardiorespiratory fitness. BWTraining to improve gait and dynamic balance post-stroke is a more recent application of this modality. Yang et al., demonstrated in people 5-7 months post-stroke that the addition of a 30-minute BWTraining to each conventional care session delivered 3x/week for three weeks resulted in a significant improved forward walking speed, stride length, and gait symmetry when compared to conventional training alone. However, with the lack of an active control group it is not known if these benefits were simply due to the additional therapy. In high-functioning stroke survivors who were able to ambulate without an assistive device or orthotic, Weng and colleagues reported that walking speed as well as balance and lower extremity motor function was significantly more improved for those in a BWTraining compared to those who received dose-matched conventional therapy. Although *total* training time was matched, these results need to be interpreted cautiously as the *amount of gait training* in the conventional therapy group was not standardized nor matched to the *amount of backward gait training*. The foundation for this current proposal resulted from our case-series with individuals post-stroke and our recently conducted pilot RCT that compared BWTraining to standard balance training in subsequent balance and gait ability Individuals in the BWTraining group demonstrated larger improvements in forward and backward gait speed, balance confidence and balance ability compared to those in dose-matched balance training group. Despite the limitations of these small prior studies, they provide enticing evidence that BWTraining may be a post-stroke gait rehabilitation strategy superior to current approaches. A current gap in the investigation of this novel rehabilitation strategy is its efficacy in reducing future fall-incidence. Secondary to the relationship between BWSpeed and fall incidence in the elderly, we hypothesize that a BWTraining would be an effective modality in decreasing falls. Specific Aim 1 will test this hypothesis. BWTraining has been assessed in both the acute and chronic post-stroke population but the effects of timing of this intervention to increase BWSpeed have not been compared directly under the rigors of a randomized controlled trial. Specific Aim 2 will test the effects of intervention timing and will provide important information regarding when BWTraining may be most beneficial for those post-stroke in increasing BWSpeed, an indicator for fall-risk.

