## **5. Specific Aims:**

**Aim #1:** Test the hypothesis that 1-year fall incidence is decreased for participants randomized to BWTraining administered at 2-months post-stroke (versus usual care comparison group).

**Hypothesis #1a:** BWTraining at 2-months post-stroke reduces the number of falls over the next year.

**Hypothesis #1b:** BWTraining at 2-months post-stroke increases gait speed, improves balance and increases balance confidence over the next year.

**Aim #2:** Test the hypothesis that BWTraining at 2 months (immediate) vs. 1-year (delayed) post-stroke is more effective at improving BWSpeed.

**Hypothesis #2a:** BWSpeed improvement from 2- to 14-months post-stroke is greater when BWTraining is delivered at 2 months versus 1 year post-stroke.

**Hypothesis #2b:** Improvements in forward gait speed, Functional Gait Assessment and Activities-Balance Confidence Scale from 2- to 14-months post-stroke are greater when BWTraining is delivered at 2 months versus 1 year post-stroke.

**Aim #3:** This exploratory aim will test the hypothesis that BWSpeed at 2-months post-stroke is a significant predictor of fall incidence over the next year 1 year period, after adjusting for other covariates.

**Hypothesis #3:** BWSpeed at 2-months will be a significant predictor of fall incidence during the first year post-stroke, after adjusting for other covariates.

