## **6. Research Plan:**

This prospective, single-blind, RCT enrolling individuals at 2-months post-stroke is designed to address the study's three Specific Aims (See Figure below). Participants will be randomized to either Immediate (2-months post-stroke) or Delayed (1-year post-stroke) BWTraining. The primary endpoint for SA#1 and SA#3 will be Assessment D at 1-year post-stroke. The primary endpoint for SA#2 will be Assessment E at approximately 14-months post-stroke. Secondary assessment time points (Assessments B and C) will allow us to examine potential mechanisms of recovery contributing to our primary results. Individual treatment allocations will be in sealed envelopes. Envelopes will be opened only on enrollment of the next eligible participant. We will recruit 142 individuals post-stroke. This will permit up to a 10% attrition rate and still provide a sufficient participant pool to address our Specific Aims.

[figure not shown]

Figure. Participants will be randomized into an Immediate (BW Training at 2-months post-stroke) or a Delayed (BW Training at 1-year post-stroke) group. Primary assessment points are A (2-months post-stroke), D (1-year post-stroke) and E. Secondary assessment points are B and C (6-months post-stroke).

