2. 10 Meter Walk Test: Participants, wearing a gait belt and guarded by a licensed physical therapist, will traverse a total distance of 14 meters, two times at their self-selected walking pace. The time to traverse the middle 10 meters will be recorded with a stop watch.
3. Lower Extremity Fugl-Meyer Motor Assessment: The participant's ability to move their paretic lower limb will be assessed in the supine, sitting and standing position.
4. Range of Motion: Range of Motion of the hips, knees and ankles of both lower limbs will be assessed. This assessment will take place in the supine and sitting positions.
5. Three-Meter Backward Walk Test. The test consists of a 1 meter warm-up distance, a timed 3 meter distance, followed by an additional 1 meter to continue walking. Participants will walk this distance two times and the speed will be averaged.

Participants who meet eligibility criteria following the screening assessment will be invited to sign Part 2 Consent, the Intervention Informed Consent Form. Intervention Informed Consent allows for baseline testing and study participation.

Following baseline assessment (Assessment A) participants will be randomized to either the Immediate Group (initiate BWTraining within 1-week of Assessment A) or the Delayed Group (initiate BWTraining at 1-year post-stroke).

BWTraining Intervention. The intervention consists of 18-21 sessions, 3x/week for 6 weeks. BWTraining will occur both on a treadmill and overground. BW training will consist of 20–30 minutes of step training with a BWST system, manual assistance provided by trainers, with rest periods provided as warranted followed by 15 minutes of overground gait training. A 20–30 min period of actual stepping on the treadmill is the goal with rest periods as needed. Each training session may last up to 1 hour and 30 minutes including time for warm-up, stretching, and cool down. Participants will be fitted with a harness around their hips and torso, which will be attached to an overhead support system directly above the treadmill. From a stationary position, the treadmill belt will gradually be increased in speed with intervention trainers assisting participant to step backward with their paretic leg, their non-paretic leg (if needed) and at the hips for weight-shift.

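### Assessments B and E, fixed at six weeks, can fall before training ends, and E at D plus six weeks is not the stated 14-month Aim 2 endpoint

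*Combined protocol and SAP*

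**What the plan says.** On the Aim 2 endpoint, Section 6 (Research Plan) states: "The primary endpoint for SA#2 will be Assessment E at approximately 14-months post-stroke". Hypothesis 2a in Section 5 reads: "BWSpeed improvement from 2- to 14-months post-stroke is greater when BWTraining is delivered at 2 months versus 1 year post-stroke". The Abstract (Methods) describes the comparison this way: "BWSpeed post-intervention will be compared between groups to assess the timing effect of BWTraining (Specific Aim #2".

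On training, the Abstract says "The intervention consists of 18 sessions (3X/week for 6 weeks) of BWTraining". Section 6, under BWTraining Intervention, says "The intervention consists of 18-21 sessions, 3x/week for 6 weeks". The Immediate group is to "initiate BWTraining within 1-week of Assessment A". The Delayed group starts at one year post-stroke, with no window after Assessment D.

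On visits, the list under Outcome Measures in Section 6 sets B at six weeks from randomization, D at one year post-stroke and E at six weeks from D, with both groups on the same calendar. Monitoring Delayed BWTraining counts B's six weeks from enrollment instead. No text links B or E to the last training session. The list refers back to the design figure, which is not in the text available to us and might clarify the timing.

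**The concern.** Three statements about one calendar do not agree: how many sessions fit into six weeks, when training may start, and when the visit meant to follow training takes place. If a site follows the six-week list literally while a Delayed participant receives 21 sessions, E is taken before that participant's training is finished. The Immediate group finished months earlier, so only the Delayed gain is cut short. The A-to-E difference then moves in the direction that Hypothesis 2a predicts.

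B is a secondary visit. An early B understates the Immediate group's response to training but does not enter the Aim 2 endpoint.

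**Working it through.** **Inputs from the documents.** Sessions: 18 (Abstract) or 18 to 21 (Section 6), three per week, six weeks. Immediate start: 0 to 7 days after A. B: day 42 from randomization. E: day 42 from D. D: 12 months. C: 6 months. Entry: 2 to 4 months post-stroke (inclusion criteria).

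**Assumptions.** Monday-Wednesday-Friday sessions starting on a Monday; randomization on the day of A; no missed sessions; 30.44 days per month; full gain G accruing evenly by session.

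**Step 1: training length.** 3 x 6 = 18, which reproduces the Abstract's figure. The upper figure in Section 6 needs 21 / 3 = 7 weeks, one more than stated.

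**Step 2: date of E.** 12 + 42/30.44 = 13.38 months. Fourteen months is 2 x 30.44 = 60.9 days, or 8.7 weeks, after D. The two dates for E differ by 60.9 - 42 = 18.9 days.

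**Step 3: visit day minus day of last session.** With n sessions (n a multiple of 3), the last falls on day 7(n/3 - 1) + 4 + lag. For n = 18 this is 39 + lag, and for n = 21 it is 46 + lag.

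| Sessions | Start lag (days) | Last session (day) | Visit on day 42 | Day 56 (week 8) | Day 60.9 (week 8.7) |
|---|---|---|---|---|---|
| 18 | 0 | 39 | +3 | +17 | +22 |
| 21 | 0 | 46 | -4 | +10 | +15 |
| 18 | 7 | 46 | -4 | +10 | +15 |
| 21 | 7 | 53 | -11 | +3 | +8 |

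A Wednesday or Friday start puts the last session one day later, so each entry drops by 1. The smallest margin is then +2 days at week 8 and about +7 (60.9 - 54 = 6.9) at week 8.7.

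All four rows apply to B, because the Immediate lag of up to a week is documented. For E only the two rows without lag follow from the documents. With 18 sessions, E is early only if 39 + lag exceeds 42, that is, with a Delayed lag of 4 days or more.

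**Step 4: share of the gain missed at day 42.** This is 1 - (sessions done)/(sessions planned), with the range depending on whether a session on day 42 comes before the visit.

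- E, 18 sessions, no lag: 0.
- E, 21 sessions, no lag: 1 - 19/21 = 0.10 to 1 - 18/21 = 0.14.
- B, no lag: the same as E.
- B, 18 sessions, one-week lag: 1 - 16/18 = 0.11 to 1 - 15/18 = 0.17.
- B, 21 sessions, one-week lag: 1 - 16/21 = 0.24 to 1 - 15/21 = 0.29.

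At E the shortfall is in the Delayed group only, so Immediate minus Delayed is too large by 0.10G to 0.14G in the affected case.

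**Step 5: room before C if B moves.** For entry at 4 months, C is 60.9 days later. B is then 19 days before C at week 6, 5 days at week 8 and 0 days at week 8.7. For entry at 3 months (91.3 days), B is still 35 days before C at week 8 and 30 at week 8.7.

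**The case against.** The best defence is that the intent is clear. The Abstract says the comparison is made after the intervention, both descriptions of training give six weeks, and with 18 sessions begun promptly there is no timing error. At about 14 months E follows training in every case above, and the design figure may settle the matter. Much of this stands: the problem at E arises only under the six-week list combined with 21 sessions or a late Delayed start. But that list is the text that sites would schedule from, and it gives neither 14 months nor any link to completion.

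Three stronger readings are tempting, and the documents do not support them.

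- **That A-to-E is a flawed endpoint because it mixes early gain with retention.** At D plus six weeks the Immediate group is 13.38 - (4 + 53/30.44) = 7.6 to 13.38 - (2 + 39/30.44) = 10.1 months past its last session, while the Delayed group is at about the end of training. But Hypothesis 2a openly defines the contrast as change to 14 months. It is a randomized comparison at a common time, and retention is part of the result. The Background's aim for this comparison ("will provide important information regarding when BWTraining may be most beneficial for those post-stroke in increasing BWSpeed") can be read in the same way. Nor is the trial unable to describe early response and retention: both groups are seen at A to E, and the plan says "Secondary assessment time points (Assessments B and C) will allow us to examine potential mechanisms of recovery contributing to our primary results". What is lacking is a written analysis; neither the Abstract nor Section 6 names a method for Aim 2.
- **That the shortfall at E could reach 0.24 to 0.29 of G.** This needs a one-week Delayed start lag, which is not in the documents.
- **That the trial's main result is affected.** Aim 1 compares fall rates at D, before E and before Delayed training.

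**Conclusion.** The inconsistency is real and of minor severity. Section 6 gives a session range that does not fit its own six weeks, and a date for E (13.4 months) that does not match its stated endpoint of about 14 months. Followed literally, with 21 sessions and no lag, E comes 4 days before the last Delayed session. That understates the Delayed gain by 0.10 to 0.14 of the full gain, in favour of Immediate. B can come 4 to 11 days early. With 18 sessions and a prompt start, both errors are zero.

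The days rest on the assumed weekday pattern, and the fractions on even accrual of gain. The documents give no expected gain in m/s, and the power calculation covers Aim 1 only, so no effect in m/s or on power can be stated. The A-to-E comparison remains valid for Hypothesis 2a.

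**What to change.** 1. Reconcile the Abstract and Section 6 (Research Plan, BWTraining Intervention, Outcome Measures, Monitoring Delayed BWTraining) on number of sessions, training length and the timing of B and E, including whether B counts from randomization or enrollment. Which training schedule is right is for the sponsor to say.
2. State that E follows the Delayed group's last session, at the same elapsed time from D in both groups, at the roughly 14 months already stated (about 8.7 weeks after D). That leaves about 7 days or more in every case considered; week 8 leaves only 2 to 3 days in the worst case. Apply the same interval from randomization to B.
3. State how soon after D the Delayed group is expected to start, so that the margin can be checked. At each visit, record the sessions completed and the date of the last one, since make-up sessions can use up the margin.
4. Keep A-to-E as the Aim 2 primary and describe it as the net benefit of early versus delayed training at about 14 months.
5. Optionally, prespecify a supportive contrast of the A-to-B and D-to-E gains between groups. It uses visits already collected, but any D-to-E change in the Immediate group enters it, so it still carries some retention. Its precision depends on the correlation structure: under compound symmetry its standard error is sqrt(4/2) = 1.41 times that of A-to-E, while under a decaying correlation it can be smaller.

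The cost is wording, with B and E 2 to 3 weeks later than the list and no new visits or participants. The downside is that B nears or coincides with C for participants enrolled at 4 months; at week 8.7 one visit could serve as both.

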**Participant Recruitment and Screening.** Priority for participation in this study will be given to volunteers who are Veterans. To optimize our capability to recruit Veterans we will conduct the study's assessments and intervention at two locations: 1) The Malcom Randall VA Medical Center in Gainesville FL, and 2) Brooks Rehabilitation in Jacksonville, FL. Utilizing these two recruitment sites will assure us of reaching our planned recruitment of 142. Individuals post-stroke will be recruited from: 1) VA BRRRC site: a. Database (IRB#457-1999) of the Malcom Randall VA BRRRC, a VA RR&D Center of Excellence. The database contains over 400 individuals with stroke who have been screened by a neurologist and interdisciplinary team to gather preliminary information about medical, motor and cognitive status. All individuals in the database have signed informed consent and agreed to be contacted for research participation. b. VA Informatics and Computing Infrastructure (VINCI) is an initiative to improve researchers' access to VA data and to facilitate the analysis of those data while ensuring Veterans' privacy and data security. c. Clinician referrals from Select Rehabilitation – potential participants will be provided an IRB-approved study flier and if interested will provide signed authorization to be contacted by study personnel. 2) Brooks site: a. Brooks Active Research Registry: Brooks Rehabilitation in Jacksonville, FL is

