*Training targets*: The overall goal is to enable the participant, by the end of training, to walk independently for a total of 20 minutes in four, 5 minute bouts at 0% BWS with good stepping kinematics. Progression of training will be accomplished by: (1) gradually decreasing BWS from 40% to 0%, (2) initiating treadmill speed just below participant's overground backward walking speed, increasing as able and as tolerated, and (3) providing manual assistance initially when the participant is unable to independently step or control upright posture, and decreasing manual assistance to afford skill and control progression by the participant.

Outcome Measures. Participants' assessments will be stored in a secured study database, password protected, accessible only to study employees. Each participant will be given a study ID with assessments recorded and stored under the study ID. Hard copy folders will be stored in a locked filing cabinet in a locked room with access only available to study personnel.

Participants in both groups will be assessed in parallel throughout the study timeline.

Assessments will be conducted five times according to the study design above:

1. Assessment A (baseline, prior to randomization)
2. Assessment B 6 weeks following randomization
3. Assessment C 6-months post-stroke
4. Assessment D 1-year post-stroke
5. Assessment E 6 weeks following Assessment D.

The assessment battery will be conducted in a 1.5 hour appointment. Assessments are similar to those encountered in physical rehabilitation and should not result in undue fatigue, but participants will be able to rest as needed. All outcome measures will be conducted by licensed physical therapists, blinded to group assignment. The physical therapist will be beside the participant during all physical assessments of gait and balance. All therapists will receive standardized training and will be required to pass a competency exam to ensure standardization of the outcome measure protocol across assessors. Assessments are:

10 Meter Walk Test. Individuals will be given a 3 meter warm-up distance for walking, preceding the 10 meter distance and 3 meters beyond the 10 meters to continue walking. The time that it takes to traverse the 10 meters at the subject's usual pace will be recorded. Participants will walk this distance two times and the speed will be averaged.

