**1. Usual and Customary Rehabilitation services:** Throughout study participation, for ethical reasons, subjects will be permitted to engage in usual and customary clinical rehabilitation services. Any rehabilitation services received outside of the study intervention will be tracked and described in written logs. All subjects will be provided a health utilization log and will complete a daily checklist to report the type (PT, OT, Speech) and the length (0.5 hr.; 0.75 hr.; 1.0 hr.). These logs will be returned (via post mail or email) on a monthly basis. Participants will receive a reminder email or phone call three days prior to the submission date. This monthly contact with those randomized to Delayed BWTraining will facilitate participant retention. Upon receipt of the intervention logs the study coordinator will call the participant to thank them. There will be no restrictions on the type of clinical rehabilitation service except that participants will be required to abstain from any that involve backward walking either over ground or on a treadmill.

**2. Falls:** As described above participants will be provided Monthly fall calendars upon enrollment, and asked to submit the monthly calendar (via post mail or email) whether they have fallen or not. Participants will receive a reminder email or phone call three days prior to the submission date. Upon receipt of the fall calendar, the study coordinator will call the participant to either: 1) thank them for returning the calendar, and/or 2) conduct a standardized questionnaire regarding fall specifics. Participants will have email and phone

access to the Study Coordinator and the Principal Investigator whom they will be instructed to contact with questions at any time.

Videorecording. For participants who signed the video recording consent, we will periodically videorecord training sessions. This will allow the intervention therapists to view the participant's training and strategize on how to progress the intervention. Videorecordings will also provide the therapists feedback on how they can best assist the participant. Assessment sessions will also be periodically recorded. This will provide assessment therapists feedback on their implementation of the assessments. Videorecordings may also be used in scientific presentations. Participants will be informed when videotaping is occurring

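### Allocation is by sealed envelope at two sites with no stated stratification by site, blocking or envelope safeguards, and the primary analysis has no site term

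*Combined protocol and SAP*

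**What the plan says.** The allocation procedure is given in two sentences of section 6, Research Plan: "Individual treatment allocations will be in sealed envelopes" and "Envelopes will be opened only on enrollment of the next eligible participant". Nothing further is stated on how the sequence is generated, whether it is blocked or stratified, whether envelopes are opaque and numbered, or who holds them.

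Under Participant Recruitment and Screening, "we will conduct the study's assessments and intervention at two locations": a VA medical center and a large rehabilitation hospital. Their recruitment routes differ: a research database, VA informatics and clinician referral at one; a registry, advertisements and inpatient record review at the other.

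On timing, the Abstract says "Following baseline assessment, participants will be randomized to BWTraining at 2 months", the Research Plan says "Following baseline assessment (Assessment A) participants will be randomized to either the Immediate Group", and the assessment list under Outcome Measures has "Assessment A (baseline, prior to randomization". Enrollment is not defined. Under Fall Incidence the calendars are issued at randomisation; under 2. Falls, "participants will be provided Monthly fall calendars upon enrollment".

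The trial is single-blind, with outcome assessors blinded. Participants or caregivers mark falls on the calendars. The Data Analysis Plan estimates one fall rate per arm and a delta-method variance per arm. Site does not appear.

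**The concern.** One arm trains at once and the other waits until a year after stroke, so participants cannot be masked, and the primary outcome is what they or their caregivers report. Blinded assessors protect the clinic tests. They do not protect the decision to enter a participant, which rests on allocation concealment, and the plan barely describes that.

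The sites may also differ in case mix, usual care and trainers. If neither allocation nor analysis accounts for site, a chance difference in site mix passes straight into the fall-rate ratio, and between-site variation stays in its variance. Both can be avoided at little cost.

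**Working it through.** **The plan's own figure.** The Power analysis assumes Poisson rates of 1.8 and 1.2 falls per year, 80% power and p = 0.05, and requires 64 per group. On the rate-difference scale, n = (1.960 + 0.842)² × (1.8 + 1.2) / 0.6² = 65.4 per group; on the square-root scale, 64.7. Simulating the planned log-ratio test 10,000 times at 64 per group gives 79.4% power. The sample size therefore reproduces closely, and nothing below changes it.

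**Chance of site imbalance.** The plan gives no site split, so three are assumed for the 142 recruits. The table shows the probability that the arms differ by at least 10 percentage points in the share from one site, without stratification. The first column is simple 1:1 allocation (exact binomial enumeration); the second fixes the arms at 71:71 (hypergeometric).

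| Assumed site split | Simple 1:1 | Arms fixed at 71:71 |
|---|---|---|
| 71/71 | 21.7% | 17.9% |
| 42/100 | 19.4% | 19.8% |
| 30/112 | 15.2% | 14.9% |

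With a 90:10 split and fixed arms the figure falls to about 5%.

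**Effect on the rate ratio.** Assume a 50:50 site split overall and a fall rate at one site R times that at the other. With a 10-point difference, the arms have 55% and 45% of their participants at the higher-rate site. The rate ratio is then multiplied by (0.55R + 0.45) / (0.45R + 0.55):

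- R = 1.5: 1.275 / 1.225 = 1.04
- R = 2: 1.55 / 1.45 = 1.07

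For a 15-point difference (57.5% and 42.5%) the factors are 1.06 and 1.11. The planned ratio is 1.2 / 1.8 = 0.67.

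**Effect on precision.** Keep the 50:50 split and Poisson counts within site. Per participant, each arm contributes (m + B) / m² to the variance of the log rate ratio, where m is the arm's mean rate and B its between-site variance. Accounting for site removes B and leaves 1/m.

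- R = 1.5: site rates are 2.16 and 1.44 (m = 1.8, B = 0.36² = 0.1296), and 1.44 and 0.96 (m = 1.2, B = 0.24² = 0.0576). The sum is 0.5956 + 0.8733 = 1.4689, against 0.5556 + 0.8333 = 1.3889 with site removed: 5% lower.
- R = 2: site rates are 2.4 and 1.2 (B = 0.6² = 0.36), and 1.6 and 0.8 (B = 0.4² = 0.16). The sum is 0.6667 + 0.9444 = 1.6111, against 1.3889: 14% lower.

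**Type I error** (10,000 simulations per setting, arms 71:71, 50:50 sites). The planned unadjusted test without stratification rejects 5.2% of the time at R = 1.5 and 5.1% at R = 2. With allocation stratified but the analysis unchanged, it rejects 4.0% and 3.4%. Stratified allocation therefore needs a matching analysis; otherwise the test is conservative and the precision gain is lost.

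**Timing words side by side.** Assessment B is six weeks after randomisation in the assessment list and six weeks after enrollment under Monitoring Delayed BWTraining. Calendars are issued at randomisation in one place and at enrollment in another. The two words name the same moment.

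**The case against.** The strongest reply is that the validity of the planned test is not at risk. Randomisation without stratification is sound, type I error stays near 5%, and the shift in the ratio is modest even under a twofold difference between sites. That stands and limits the point to precision, chance balance and concealment. The plan is also silent rather than explicit, so blocking or stratification may be intended. That stands too: the defect is that nothing is stated.

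The documents do not support four stronger readings.

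- A reader might infer that opening envelopes on enrollment contradicts randomising after baseline, so that Assessment A is done with the arm known. That requires enrollment to mean signing the intervention consent, which no section says. Three places put baseline first, and the two words are used for one event.
- A reader might picture a single run of envelopes shared by both sites. The plan does not say how the envelopes are organised.
- A reader might suppose that recruiting or training staff open them. No section says who does.
- A reader might fear that unequal arms undermine the 64 per group. On the log-rate scale, power is Φ(ln 1.5 / √[1/(1.8 n₁) + 1/(1.2 n₂)] − 1.96), with n₁ in the higher-rate arm and n₂ in the lower. With all 142 followed for a year, arms of 63 and 79 give 83.0% or 81.3%, depending on which arm is smaller, against 78.6% at 64/64. The harm is negligible.

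**Conclusion.** The concern holds as a gap in design and analysis. The stated method is sealed envelopes in an unmasked two-site trial with self-reported falls, with no stated stratification, blocking or safeguard and no site term in the primary estimator. A 10-point difference in site share has a probability of about 15% to 22% at the assumed splits. It would move the rate ratio by about 4% to 7% if site fall rates differ 1.5- to 2-fold. Removing site variation would cut the variance of the log rate ratio by about 5% to 14% under the same assumptions.

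The site splits and between-site rate ratios are assumptions, and the variance figures also assume Poisson counts within site. If the sites have similar fall rates, the balance and precision gains shrink towards zero and the case rests on concealment. The timing wording is loose rather than contradictory and needs only a definition.

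**What to change.** 1. In the Research Plan, replace the envelope rule with computer-generated 1:1 allocation, stratified by site, in permuted blocks of varying size, released only after Assessment A is recorded.
2. In the Data Analysis Plan, compute the log rate ratio and its delta-method variance within each site, and combine the two estimates with a weighting rule fixed in advance.
3. In the envelope sentence and the fall-calendar text, replace enrollment with randomisation (after Assessment A). Start calendars and time at risk at that moment; the Data Analysis Plan does not say when time at risk begins.

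The cost is protocol wording and one set-up task, with no added patients or visits and no change to the stated sample size. It depends on the study database, or an equivalent system, being able to release allocations; the protocol says only that the database is secured, password protected and stores assessments. Staff will need access to it at the moment of randomisation.
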